10.4.2. Contraception Guidance

10.4.2.1. Female Participants

Female participants of non-childbearing potential are exempt from contraception requirements. Female participants of childbearing potential, if heterosexually active, must use highly effective contraception as defined below. Antibiotic prophylaxis may be administered during this study (see Section 8.2.9), which can compromise the efficacy of hormonal contraception. Therefore, participants using hormonal contraception must also use barrier contraception (eg, condom or diaphragm with spermicide) for the duration of antibiotic prophylaxis.

Highly effective contraceptive methods for females are as follows:

- Combined (estrogen- and progestogen-containing) hormonal contraception associated with inhibition of ovulation as follows:
 - Oral

- Intravaginal
- Transdermal
- Progestogen-only hormonal contraception associated with inhibition of ovulation as follows:
 - Oral
 - Injectable
 - Implantable
- Intrauterine device
- Intrauterine hormone-releasing system
- Bilateral tubal occlusion
- Vasectomized male partner (with documented evidence of azoospermia if possible)
- Sexual abstinence (in line with the preferred and usual lifestyle of the participant)

Sexual abstinence is considered a highly effective method only if defined as refraining from heterosexual intercourse during the entire period of risk associated with the study treatments. Calendar, ovulation, symptothermal, post-ovulation methods, and withdrawal do NOT meet the definition of abstinence. The reliability of sexual abstinence needs to be evaluated in relation to the duration of the clinical trial and the preferred and usual lifestyle of the participant.

Participants must use an appropriate form of highly effective contraception as stated for females of childbearing potential who are sexually active, from one complete menstrual cycle prior to the first intercourse with a male and continue until for at least 5 months after last dose.

10.4.2.2. Male Participants

To prevent transfer of study drug to a male or female partner or fetus/baby, all male participants including those who have had a vasectomy (even with documented evidence of azoospermia) must agree to use a barrier method (male condom) during intercourse with a male or female partner from the time of screening for at least 5 months after last dose.

Male participants, if sexually active and with a female spouse or partner of childbearing potential or a pregnant or breastfeeding spouse or partner, must agree to use barrier contraception (male condom). Barrier contraception is required even with documented medical assessment of surgical success of a vasectomy. Female spouses or partners of male participants who are of childbearing potential must use highly effective contraception as defined above.

Contraception for all cohorts must start during Screening and continue for at least 5 months after last dose.

Male participants must not donate sperm and female participants must not donate ova for at least 5 months after last dose.

10.4.3. Collection of Pregnancy Information

- Pregnancy data will be collected during this study for all female participants and any female spouse/partner of a male participant, who become pregnant. Exposure during pregnancy (also referred to as exposure in utero) can be the result of either maternal exposure or transmission of drug product via semen following paternal exposure.
- If a female participant or a male participant's female sexual partner of childbearing potential becomes or is found to be pregnant while being treated or exposed to study drug, the Investigator must submit the "Pregnancy Reporting and Outcome/Breastfeeding" form to Alexion or designee via the same method as SAE reporting (Section 10.3). When the outcome of the pregnancy becomes known, the form should be updated and submitted to Alexion or designee. If additional follow-up is required, the Investigator will be requested to provide the information.
- Exposure of an infant to a Sponsor product during breastfeeding must also be reported (via the "Pregnancy Reporting and Outcome Form/Breastfeeding" form) and any AEs experienced by the infant must be reported to Alexion or designee via facsimile or email.
- A pregnancy in and of itself is not regarded as an AE unless there is a suspicion that the study drug may have interfered with the effectiveness of a contraceptive medication. However, complications of pregnancy and abnormal outcomes of pregnancy are AEs and may meet the criteria for an SAE (eg, ectopic pregnancy, spontaneous abortion, intrauterine fetal demise, neonatal death, or congenital anomaly). Elective abortions without complications should not be reported as AEs (Section 8.2.6).
- Any female participant who becomes pregnant while participating in the study will be withdrawn from the study.

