Table 5: Schedule of Activities – Day 8 Through Day 127 for Single-dose Cohorts 1 - 7

Study Day ^a	Day 8 (168 h post SOI)	Day 15	Day 22	Day 29	Day 36	Day 43	Day 50	Day 57	Day 71	Day 85	Day 99	Day 127 ^h /ET
Window (days)	0	±1	±1	±1	±1	±1	±1	±1	±1	±1	±1	±1
Status (OP or CRU)	OP	OP	OP	OP	OP	OP	OP	OP	OP	OP	OP	OP
Physical examination	X			X								X
Vital sign measurements	X	X	X	X	X	X	X	X	X	X	X	X
Triplicate ECG	X	X		X				X	X		X	X
Chemistry ^b	X			X				X				X
Hematology	X			X				X				X
Coagulation	X			X				X				X
Urinalysis (via dipstick)	X			X				X				X
Serum pregnancy test				X				X		X		X
PK samples	X	X	X	X	X	X	X	X	X	X	X	X
PD panel (serum total and free properdin, CAP activity)	X	X	X	X	X	X	X	X	X	X	X	X
Exploratory biomarkers ^c		X		X								X
Immunogenicity (ALXN1820 ADA) ^e		X		X				X		X		X ^d
Review safety card ^f	X	X	X	X	X	X	X	X	X	X	X	X
Concomitant medications	←Monitor continuously→											
Adverse events ^g	←Monitor continuously→											
Prophylactic antibiotic tx ^h	←Antibiotic prophylaxis→											

^a Permissible windows for study assessments are described in the Study Operations Manual.

^b Non-fasting blood samples will be obtained.

^c Collection of blood (for serum, citrated and K2-EDTA, or Plasma P100 plasma) and urine.

^d Participants who are ADA positive at Day 127/ET will be followed up to 1 year from the study drug administration or ADA titers return to baseline levels (whichever occurs first).

^e In case of any suspected case of hypersensitivity or anaphylaxis additional samples for the assessment of ADA may be collected at or near the event.

^f The Investigator or qualified designee will meet with the participant at each visit to ensure they carry the clinical study participant safety card at all times and to review the potential meningococcal infection risks of ALXN1820, and to address any safety concerns on the part of the participant

^g Collection of adverse events and serious adverse events will begin after ICF signing.

^h Participants will be administered prophylactic antibiotic treatment, oral penicillin V 500 mg twice daily (equivalent to 1×10^6 units), beginning on the evening of Day -1 through Day 127, or until complement activity has normalized (as determined by CAP assay). If penicillin is not tolerated, second line antibiotics will be initiated at the discretion of the Investigator. Follow-up will be extended until individual CAP activity has normalized.

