7. DISCONTINUATION OF STUDY INTERVENTION AND PARTICIPANT DISCONTINUATION/WITHDRAWAL

7.1. Discontinuation of Study Intervention

In rare instances, it may be necessary for a participant to permanently discontinue (definitive discontinuation) the study intervention. If the study intervention is definitively discontinued, the participant should remain in the study to be evaluated for safety follow-up. See the SoA for data to be collected at the time of discontinuation of study intervention and follow-up and for any further evaluations that need to be completed.

Participants should be considered for discontinuation from intervention if any of the following occur during the study:

- Serious hypersensitivity reaction;
- Severe uncontrolled infection;
- Use of disallowed medication as defined in Section 6.5;
- Pregnancy or planned pregnancy; or
- Alexion or the Investigator deems it is necessary for the participant.

See the SoA for data to be collected at the time of intervention discontinuation and follow-up and for any further evaluations that need to be completed.

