7.3. Participant Discontinuation/Withdrawal From the Study

All efforts should be made to ensure participants are willing to comply with study participation prior to conducting the screening procedures. The study staff should notify Alexion and their site monitor of all study withdrawals as soon as possible. The reason for participant discontinuation must be recorded in the source documents and eCRF.

A participant may withdraw from the study at any time at his/her own request, or may be withdrawn at any time at the discretion of the Investigator for safety, behavioral, compliance, or administrative reasons. This is expected to be uncommon.

At the time of discontinuing from the study, if possible, an early discontinuation visit should be conducted, as shown in the SoA. See SoA (Section 1.3) for data to be collected at the time of study discontinuation and follow-up and for any further evaluations that need to be completed.

The participant will be permanently discontinued both from the study intervention and from the study at that time.

If the participant withdraws consent for disclosure of future information, Alexion may retain and continue to use any data collected before such a withdrawal of consent.

If a participant withdraws from the study, he/she may request destruction of any samples taken and not tested, and the Investigator must document this in the site study records.

In order to meet minimum data requirements for SRC meetings, participants who withdraw consent from the study within the first 14 days may be replaced. At the Sponsor's discretion, and after consultation with the SRC, up to 18 additional participants may be enrolled as replacement participants if a participant discontinues prior to Day 43 for reasons other than drug-related AEs.

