8.2.6. Pregnancy

No studies of ALXN1820 have been conducted in pregnant women. Pregnant or breastfeeding females are excluded from the clinical study. Participants enrolled in the study, and a spouse or partner, will use a highly effective or acceptable method of contraception. Refer to Section 10.4 for additional details.

Following the last study visit, female participants are required to perform a monthly pregnancy test until at least 5 months after the last dose. For the convenience of the participant, a serum sample will be collected when there is a clinic visit, otherwise, urine test need to be done at home (when there is no clinic visit) and the result is to be reported to the Sponsor within 3 days.

Pregnancy data from female participants and female spouses/partners of male participants will be collected from the signing of the ICF until the outcome of the pregnancy is known, which might occur after the last follow-up visit. Any female participant who becomes pregnant while participating in the study will be discontinued from the study intervention. If a pregnancy is reported, the Investigator must immediately inform Alexion within 24 hours of awareness of the pregnancy and follow the procedures outlined in Section 10.4.

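### Protocol Section 10.4.3 withdraws a participant who becomes pregnant from the study, while Section 7.1 keeps her in for safety follow-up and Section 8.2.6 stops only the study drug

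*Protocol*

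**What the plan says.** Three places in the protocol deal with a participant who becomes pregnant.

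- **Section 7.1** names pregnancy among the events for which stopping the intervention should be considered. Of anyone whose intervention is definitively stopped it says that "the participant should remain in the study to be evaluated for safety follow-up".
- **Section 8.2.6** makes the drug stop mandatory: "Any female participant who becomes pregnant while participating in the study will be discontinued from the study intervention". It says nothing about leaving the study. It then requires that "the Investigator must immediately inform Alexion within 24 hours of awareness of the pregnancy and follow the procedures outlined in Section 10.4".
- **Section 10.4.3**, reached by that cross-reference, closes with "Any female participant who becomes pregnant while participating in the study will be withdrawn from the study".

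Section 7.3 sets out what leaving the study means. An early discontinuation visit is held if possible, and "The participant will be permanently discontinued both from the study intervention and from the study at that time". The section also refers to the Schedule of Activities for "data to be collected at the time of study discontinuation and follow-up and for any further evaluations that need to be completed".

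In that schedule, footnote h of Tables 5, 8 and 11 covers prophylaxis. In Table 5 it ends: "Follow-up will be extended until individual CAP activity has normalized". Section 8.2.9 continues antibiotics in every member of a cohort until complement activity has normalized in all of them, to protect the blind.

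**The concern.** Withdrawal from the study and retention for safety follow-up are different instructions, and the protocol gives both for the same event. The cross-reference in Section 8.2.6 leads the site to the withdrawal rule.

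Withdrawal also gains little. In the single-dose cohorts no dose remains to be withheld. In the multiple-dose cohorts the drug stop in Section 8.2.6 already prevents further exposure. What withdrawal adds is the end of participation. Section 8.3.1 collects adverse events up to the last follow-up visit and does not oblige investigators to seek them actively afterwards. The scheduled vital signs, laboratory and CAP assessments would also stop after the early termination visit.

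At stake is the follow-up of a pregnant woman exposed to a first-in-human complement inhibitor, over weeks in which the protocol's own model may still predict inhibition.

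**Working it through.** **Step 1. The texts side by side.**

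| Section | Study drug | Participation |
|---|---|---|
| 7.1 | Consider stopping | Should remain for safety follow-up |
| 8.2.6 | Must stop | Not stated; refers to 10.4 |
| 10.4.3 | Not stated separately | Must be withdrawn |

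Sections 7.1 and 8.2.6 can both be followed. Section 8.2.6 taken alone fits either outcome. Sections 7.1 and 10.4.3 cannot both be followed. The clash is most direct between doses in Cohorts 8 to 10, where there is still drug to discontinue. In Cohorts 1 to 7, and after the last multiple dose, Section 7.1 applies by its evident intent more than by its letter.

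**Step 2. How much predicted inhibition can remain.** The inputs are the CAP columns of Table 16 and the pregnancy-test days in Tables 5, 7 and 8. Dosing is on Day 1, so days elapsed = visit day − 1. The protocol's own pairing of Day 29 with 672 hours agrees: 672 / 24 = 28.

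Days left = predicted duration from first dose − (visit day − 1).

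| Case | Complete CAP inhibition | Return to 80% of baseline |
|---|---|---|
| Cohort 4, Day 29 | 39 − 28 = 11 | 54 − 28 = 26 |
| Cohort 5, Day 29 | 39 − 28 = 11 | 53 − 28 = 25 |
| Cohort 6, Day 29 | 67 − 28 = 39 | 84 − 28 = 56 |
| Cohort 6, Day 57 | 67 − 56 = 11 | 84 − 56 = 28 |
| Cohorts 8 and 9, Day 7, one dose given (Cohort 3 prediction) | 16 − 6 = 10 | 26 − 6 = 20 |
| Cohorts 8 and 9, Day 36, five doses given | 66 − 35 = 31 | 83 − 35 = 48 |

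Table 16 allows a cross-check of the last row. It also gives 38 and 55 days counted from the fifth dose, which falls on Day 29. Day 36 is 7 days later: 38 − 7 = 31 and 55 − 7 = 48, the same results.

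**Step 3. Where nothing is predicted to remain.** At Day 29, Cohorts 1 to 3 have already returned to 80% (0, 9 and 26 days, all below 28). At Day 57, so have Cohorts 4 and 5 (54 and 53, below 56). At Day 85, Cohort 6 is at 84 − 84 = 0, and Cohorts 8 and 9 are past it (83, below 84). Table 16 has no prediction for two to four weekly doses, and the Cohort 10 dose is still to be determined.

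These are predicted days of drug effect after a positive scheduled test in a participant on active drug. They are not days without protection.

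**The case against.** The strongest reply is that a site following the cross-reference arrives at one specific, mandatory instruction, while Section 7.1 is general and uses softer verbs. That may predict what a site would do, but it does not reconcile the two sections, and the outcome is the less protective one.

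Three stronger readings are tempting, and the documents support none of them.

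*That withdrawal leaves her unprotected.* Sections 2.3.1.1 and 8.2.9 require prophylaxis until complement activity normalizes. The sponsor is told within 24 hours. Section 8.2.6 collects pregnancy data until the outcome is known, and Section 10.4.3 treats complications and abnormal outcomes as adverse events. Section 8.3 still requires follow-up of serious, related or discontinuation-causing events.

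*That CAP follow-up certainly ends at early termination.* Section 7.3 refers to the schedule for further evaluations, and in Tables 5 and 8 footnote h is marked on the combined final-visit and early-termination column. It can fairly be read as reaching early terminators, although its text does not say so. The antidrug antibody footnotes in the same tables do name early termination and set a limit of 1 year. The lack of a dated CAP sample after the final visit affects ordinary completers too, so it is not a consequence of the pregnancy rule.

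*That withdrawal adds a calculable number of antibiotic days.* Section 8.2.9 ties stopping to the slowest member of the cohort, so even a retained participant would not stop on her own result. Comparing the default end of prophylaxis with her own predicted recovery does not measure the effect of Section 10.4.3.

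**Conclusion.** The conflict between Sections 10.4.3 and 7.1 is real, and Section 8.2.6 is out of step with 10.4.3. Following 10.4.3 could end active adverse event collection and scheduled CAP visits with up to 39 predicted days of complete inhibition and 56 days to 80% of baseline remaining (Cohort 6, Day 29), among the cases worked above.

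The figures rest on the Table 16 model predictions, on active treatment, and on detection at a scheduled test. A placebo recipient has no drug effect left, and later detection shortens the remainder.

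The point is minor. The event should be rare given the contraception rules in Section 10.4.2, and the protective measures continue. No planned analysis is materially affected: SAP Section 7.3 uses data up to discontinuation, so the loss is one participant's later time points. The change is still worth making, because it improves safety follow-up at little cost.

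**What to change.** Replace the last bullet of Protocol Section 10.4.3 with:

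> Any female participant who becomes pregnant will be discontinued from the study intervention and, unless she withdraws consent, will remain in the study for safety follow-up per Section 7.1, with the scheduled AE and CAP assessments through Day 127 or Day 155, extended if CAP activity has not normalized by then; antibiotic prophylaxis continues per Section 8.2.9, including its cohort-wide stopping rule, with the choice of agent left to the Investigator and Sponsor.

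Naming Day 127 or Day 155 prevents a reading in which adverse event follow-up stops once CAP recovers. Pointing to the cohort-wide rule prevents a placebo recipient with normal CAP from stopping antibiotics early and revealing her assignment.

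The cost is a small wording amendment, which needs IRB/IEC approval before implementation under Section 10.1.1. It adds no visits beyond the existing schedule and its extension rule. It does not supply a dated CAP sample after the final visit; that is a general matter for footnote h.

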10.5. Appendix 5: Biomarkers

- Whole blood samples will be collected for biomarker analyses and the data will be used for research (eg, exploratory) related to ALXN1820. The samples may also be used to develop tests/assays including diagnostic tests related to ALXN1820 and/or others of this study intervention class.
- The samples may be analyzed as part of a multistudy assessment of biomarkers in the response to ALXN1820 to understand study disease or related conditions. Analyses may be done to establish normal range of values for biomarkers which may include, but are not limited to, markers of complement dysregulation (eg, Factor Ba), vascular inflammation (eg, soluble tumor necrosis factor receptors), and endothelial activation/damage (eg, soluble vascular cell adhesion molecule-1, thrombomodulin).
- The results of biomarker analyses may be reported in the clinical study report or in a separate study summary.
- Alexion or designee will store the samples obtained for biomarker analyses in a secure storage space with adequate measures to protect confidentiality.
- The samples will be retained while research on ALXN1820 continues but no longer than 5 years or other period as per local requirements.

10.6. Appendix 6: Management of Potential Adverse Events During Study Drug Administration

Infusion/injection-associated reactions are a potential risk with the use of therapeutic protein products; these reactions can be nonimmune or immune mediated (eg, hypersensitivity reactions). Signs and symptoms may include headache, fever, facial flushing, pruritus, myalgia, nausea, chest tightness, dyspnea, vomiting, erythema, abdominal discomfort, diaphoresis, shivers, hypertension, lightheadedness, hypotension, palpitations, and somnolence. Signs and symptoms of hypersensitivity or allergic reactions may include hives, swollen face, eyelids, lips, or tongue, or trouble with breathing. An acute infusion reaction algorithm will be used to manage infusion-associated reactions (See Study Operation Manual).

All infusion/injection-associated reactions will be reported to the Investigator and qualified designee. The Investigator and qualified designee are responsible for detecting, documenting, and recording events that meet the definition of AE or SAE and remain responsible for following up events that are serious, considered related to the study drug or study procedures, or that caused the participant to discontinue ALXN1820.

Definitions and procedures for recording, evaluating, follow-up, and reporting AEs and SAEs are outlined in Section 10.3.

Before study drug administration, the treating physician and other appropriate personnel must make certain that medication (ie, adrenaline, inhaled beta agonists, antihistamines, corticosteroids) and other equipment to treat anaphylaxis are readily available. The infusion must be stopped immediately if Grade ≥ 3 allergic/hypersensitivity reactions (including drug fever) or Grade ≥ 3 cytokine release syndrome/acute infusion reaction occurs. Alexion must be notified within 24 hours of any infusion reaction requiring interruption or discontinuation of study drug. Participants who experience a reaction during the administration of study drug should be treated according to institutional guidelines.

For a Grade 2 infusion reaction, the infusion should be temporarily stopped and treatment with an antihistamine and acetaminophen/paracetamol/NSAIDs may be considered. If the participant's signs and symptoms have resolved (with or without administration of the above medication), the infusion may be restarted. However, the participant should be infused at a slower rate and be monitored closely for any signs and symptoms of infusion reactions during the remainder of the infusion. Participants experiencing an infusion reaction should be observed in the clinic until resolution of the reaction, or until the Investigator determines the participant is no longer at risk. Participants who experience a severe reaction during administration of study drug resulting in discontinuation of study drug should undergo all scheduled safety, PK, and PD evaluations required by the protocol, if possible.

If anaphylaxis occurs, please follow local guidance for the management. In the event that there is no local guidance, please see suggested management as follow:

Administration of epinephrine (1/1000, 0.3 mL to 0.5 mL, or equivalent) should be considered. In the case of bronchospasm, treatment with an inhaled beta agonist also should be considered. Participants administered an antihistamine for the treatment or prevention of an infusion reaction should be given appropriate warnings about drowsiness and impairment of driving ability before being discharged from the center.

Table 24: Grading and Management of Allergic or Infusion-Related Reactions

Adverse Event	Grade				
	1	2	3	4	5
Infusion-related reaction	Mild transient reaction; infusion interruption not indicated; intervention not indicated	Therapy or infusion interruption indicated but responds promptly to symptomatic treatment (eg, antihistamines, non-steroidal anti-inflammatory drugs [NSAIDs], narcotics, IV fluids): prophylactic medications indicated for ≤ 24 hours	Prolonged (eg, not rapidly responsive to symptomatic medication and/or brief interruption of infusion); recurrence of symptoms following initial improvement, hospitalization indicated for clinical sequelae	Life-threatening consequences; urgent intervention required	Death
Allergic reaction	Transient flushing or rash, drug fever < 38.0°C. Intervention not indicated	Therapy or infusion interruption indicated but responds promptly to symptomatic treatment (eg, antihistamines, NSAIDs, narcotics, IV fluids): prophylactic medications indicated for ≤ 24 hours	Prolonged (eg, not rapidly responsive to symptomatic medication and/or brief interruption of infusion); recurrence of symptoms following initial improvement, hospitalization indicated for clinical sequelae (eg, renal impairment, pulmonary infiltrates)	Life-threatening consequences; urgent intervention required	Death
Anaphylaxis	–	–	Symptomatic bronchospasm, with or without urticarial; parenteral intervention indicated; allergy-related edema/angioedema; hypotension	Life-threatening consequences; urgent intervention required	Death
Cytokine release syndrome	Mild reaction: infusion interruption not indicated; intervention not indicated	Therapy or infusion interruption indicated but responds promptly to symptomatic treatment (eg, antihistamines, NSAIDs, narcotics, IV fluids): prophylactic medications indicated for ≤ 24 hours	Prolonged (eg, not rapidly responsive to symptomatic medication and/or brief interruption of infusion); recurrence of symptoms following initial improvement, hospitalization indicated for clinical sequelae (eg, renal impairment, pulmonary infiltrates)	Life-threatening consequences; pressor or ventilator support indicated	Death

Abbreviations: IV = intravenous; NSAIDs = nonsteroidal anti-inflammatory drugs
Source: NCI CTCAE Version 5.0.

